### **5.2.1. Data Handling After the Cut-off Date**

Data after the cut-off date may not undergo the cleaning process and will not be displayed in any listings or used for summary statistics, statistical analyses or imputations.

### **5.2.2. Pooling of Centers**

In order to provide overall estimates of treatment effects, data will be pooled across centers. The 'center' factor will not be considered in statistical models or for subgroup analyses due to the high number of participating centers in contrast to the anticipated small number of patients randomized/treated at each center.

### **5.2.3. Presentation of Continuous and Qualitative Variables**

Continuous variables will be summarized using descriptive statistics ie, number of non-missing values and number of missing values [ie, n (missing)], mean, median, standard deviation (SD), minimum, maximum and first and third quartile (Q1 and Q3).

Qualitative variables will be summarized by frequency counts and percentages. Unless otherwise specified, the calculation of proportions will include the missing category. Therefore counts of missing observations will be included in the denominator and presented as a separate category.

In case the analysis refers only to certain visits, percentages will be based on the number of patients still present in the study at that visit, unless otherwise specified.

### **5.2.4. Definition of Study Day**

Start day of study treatment is the day of the first dose of study treatment.

The study day for assessments occurring on or after the start of study treatment (eg, adverse event onset, tumor measurement) will be calculated as:

$$\text{Study day} = \text{Date of the assessment/event} - \text{start of study treatment} + 1.$$

The study day for assessments occurring prior to the first dose of study treatment (eg, baseline characteristics, medical history) will be negative and calculated as:

$$\text{Study day} = \text{Date of the assessment/event} - \text{start of study treatment}.$$

The study day will be displayed in all relevant data listings.

### **5.2.5. Definition of Start of New Anti-cancer Drug Therapy**

Start date of new anti-cancer drug therapy is used to determine the end of the on-treatment period (see [Section 5.2.7](#)).

The start date of new anti-cancer drug therapy is the earliest start date of anti-cancer drug therapy recorded in the 'Prior and Concomitant Drug Treatment' eCRF page that is after the first dose of study treatment. This date will be identified based on clinical review.

### 5.2.6. Definition of Start of New Anti-cancer Therapy

Start date of new anti-cancer therapy (drug, radiation, surgery) is used for censoring in efficacy analyses (see [Section 6.2.2](#)).

The start date of new anti-cancer therapy is the earliest date after the ‘start date’ amongst the following:

- Start date of anti-cancer drug therapy as identified in [Section 5.2.5](#).
- Start date of radiation therapy as identified by clinical review based on data recorded in the ‘Prior and Concomitant Non-drug Treatment’ eCRF page
- Surgery date recorded in ‘Concomitant Surgery’ when “Surgery Outcome” = ‘Resected’ or ‘Partially Resected’.

When start date of anti-cancer therapy is missing or partially missing, the imputation rules described in [Section 5.3.3.4](#) should be applied.

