4.1. Inclusion Criteria

Patients must meet all of the following inclusion criteria to be eligible for enrollment into the study:

1. Histological or cytological diagnosis of advanced/metastatic solid tumor malignancy which has progressed on standard therapy or for which no standard therapy is available.
2. Measurable disease per RECIST v1.1.
3. Expansion cohort patients must have tumor accessible for sequential biopsy (core needle biopsy or excision preferred).
4. Age 18 years or older.
5. Eastern Cooperative Oncology Group (ECOG) performance status of 0 or 1 (see [Appendix 2](#)).
6. Adequate bone marrow function, defined as absolute neutrophil count (ANC) $\geq 1.5 \times 10^9/L$ ($\geq 1,500/\mu L$), platelet count $\geq 100 \times 10^9/L$ ($\geq 100,000/\mu L$), and hemoglobin $> 9.0 \text{ g/dL}$ ($> 5.6 \text{ mmol/L}$). Patients must be transfusion independent (ie, no blood product transfusions for a period of at least 14 days prior to study registration).
7. Adequate renal function, including serum creatinine $\leq 1.5 \times$ upper limit of normal (ULN) or estimated creatinine clearance $\geq 60 \text{ mL/min}$ as calculated using the method standard for the institution.
8. Adequate liver function, including: Total serum bilirubin $\leq 1.5 \times$ ULN (unless the patient has documented Gilbert syndrome), Aspartate and Alanine Aminotransferase (AST and ALT) $\leq 2.0 \times$ ULN, Alkaline phosphatase $\leq 2.5 \times$ ULN; ($\leq 5 \times$ ULN in case of bone metastasis).
9. Resolved acute effects of any prior therapy to baseline severity or Grade ≤ 1 CTCAE except for AEs not constituting a safety risk by investigator judgment.
10. Serum/urine pregnancy test (for females of childbearing potential) negative at screening and at the baseline visit (before the patient may receive the investigational product).
11. Male and female patients of childbearing potential must agree to use two (2) highly effective methods of contraception throughout the study and for 120 days after the last dose of assigned treatment.

Female patients who are not of childbearing potential (ie, meet at least one of the following criteria):

- Have undergone a documented hysterectomy and/or bilateral oophorectomy;
 - Have medically confirmed ovarian failure or;

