7.6. Tumor Biopsies for Mechanistic Exploratory Biomarkers

Tumor growth inhibition following treatment with 4-1BB agonist monoclonal antibodies or with PD-1 antagonist monoclonal antibodies has been associated with increases in tumor-infiltrating lymphocytes. Paired de novo tumor biopsies are mandatory for the patients enrolled in the expansion cohorts in order to determine whether the combination of PF-05082566 and MK-3475 has this effect. A de novo biopsy will be required at study entry followed by a second biopsy at the time of the Cycle 3 tumor assessment. For patients in dose escalation cohorts, unscheduled optional de novo tumor biopsies may be collected at the discretion of the Sponsor and Investigator to support the assessment of disease progression. Biomarkers that will be assayed may include but will not be limited to IHC assessment of tumor-infiltrating lymphocytes, PD-L1 IHC, quantitation of T cell receptor sequences, and gene expression.

Please refer to the Study Manual for details pertaining to specific days of sample collection, and sample preparation and shipping

CCI

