##### 6.2.2.1. Objective Response as Assessed by the Investigator per RECIST v1.1

The following analyses will be based on the FAS by treatment group. Assessment of response will be made using RECIST v1.1.

**Best Overall Response (BOR)** will be assessed based on reported overall lesion responses at different evaluation time points from the ‘start date’ until documented disease progression, according to the following rules:

- CR = at least two determinations of CR at least 4 weeks apart and before progression.
- PR = at least two determinations of PR or better at least 4 weeks apart and before progression (and not qualifying for a CR).
- SD (applicable only to patients with measurable disease at baseline) = at least one SD assessment (or better)  $\geq 6$  weeks after ‘start date’ and before progression (and not qualifying for CR or PR).
- Non-CR/non-PD (applicable only to patients with non-measurable disease at baseline) = at least one non-CR/non-PD assessment (or better)  $\geq 6$  weeks after ‘start date’ and before progression (and not qualifying for CR or PR).

- PD = progression  $\leq 12$  weeks after start date (and not qualifying for CR, PR SD, or non-CR/non-PD).
- Not Evaluable (NE): all other cases.

Only tumor assessments performed before the start of any further anti-cancer therapies will be considered in the assessment of BOR. Clinical deterioration will not be considered as documented disease progression.

**Objective Response (OR)** is defined as complete response (CR) or partial response (PR) according to RECIST v1.1 from start date until documented disease progression. Both CR and PR must be confirmed by repeat assessments performed no less than 4 weeks after the criteria for response are first met.

Patients who do not have an on-treatment radiographic tumor assessment (including due to early clinical progression), who receive anti-tumor treatments other than the study treatments prior to reaching a CR or PR, or who die, progress, or drop out for any reason prior to reaching a CR or PR will be counted as non-responders in the assessment of OR. Each patient will have an objective response status (0: no OR; 1: OR). OR rate (ORR) is the proportion of patients with OR in the analysis set.

ORR by treatment group will also be calculated along with the two-sided 95% CI using the Clopper-Pearson method (exact CI for a binomial proportion as computed by default by the FREQ procedure using the EXACT option).

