#### **6.5.5. Subsequent Anti-cancer Therapies**

Anti-cancer treatment will be provided in a data listing with data retrieved from 'Concomitant Drug Treatment', 'Prior and Concomitant Non-drug Treatment' and 'Concomitant Surgery' eCRF pages based on clinical review.

The earliest date of start of new anti-cancer drug therapy after 'start date' will be used for the definition of the on-treatment period and the earliest date of start of new anti-cancer therapy after 'start date' will be used for the censoring for efficacy analyses (see [Section 5.2.5](#) and [5.2.6](#)).

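### SAP 5.2.6 counts any surgery coded Resected or Partially Resected as new anti-cancer therapy without clinical review, so a recorded excisional biopsy could wrongly censor PFS and DR and lose an unconfirmed response

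*SAP*

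**What the plan says.** SAP 5.2.6 states the purpose of the date: "Start date of new anti-cancer therapy (drug, radiation, surgery) is used for censoring in efficacy analyses". It is the earliest of three components.

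- **Drug**, taken from 5.2.5: "This date will be identified based on clinical review".
- **Radiation**: "Start date of radiation therapy as identified by clinical review based on data recorded in the" non-drug treatment page.
- **Surgery**: "Surgery date recorded in ‘Concomitant Surgery’ when “Surgery Outcome” = ‘Resected’ or ‘Partially Resected".

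The first two components are conditioned on clinical review. The third depends on one coded field.

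SAP 6.5.5 describes a listing of anti-cancer treatment drawn from the drug page and from "Prior and Concomitant Non-drug Treatment' and 'Concomitant Surgery' eCRF pages based on clinical review". Its next paragraph turns to the censoring date and refers back to 5.2.5 and 5.2.6.

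The date is used in two ways. SAP 6.2.2.1 says "Only tumor assessments performed before the start of any further anti-cancer therapies will be considered in the assessment of BOR". SAP 6.2.2.5 and Table 3 censor PFS and DR at the last adequate scan before the new therapy.

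In the protocol, section 7.6 says "Paired de novo tumor biopsies are mandatory for the patients enrolled in the expansion cohorts", and footnote 34 of the Schedule of Activities places the second biopsy at the week-9 scans. Inclusion criterion 3 reads "Expansion cohort patients must have tumor accessible for sequential biopsy (core needle biopsy or excision preferred".

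**The concern.** Two of the three components leave room for a judgement on whether the treatment was given against the cancer. The surgery component does not. A programmer working from 5.2.6 would flag every qualifying record, including a diagnostic excision.

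That kind of record is foreseeable. PFS, DR and time to response are analysed only in the expansion cohorts, and those are the patients who must have an on-treatment biopsy, with excision among the preferred methods. Nothing in either document exempts a study biopsy from the surgery rule. Protocol 7.9 only removes a lesion biopsied after treatment from the target set; it does not end follow-up for response or progression.

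At stake are PFS, DR, best overall response and the tumour-shrinkage summary, which also drops scans after subsequent therapy (SAP 6.2.2.2). Table 4 ranks new anti-cancer therapy second among the censoring reasons, so a biopsy could be reported under that label. Safety summaries are not affected, because the on-treatment period in SAP 5.2.7 uses the drug-therapy date only.

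**Working it through.** The plan gives no figure for this rule, so the check is to trace a patient through it.

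**Inputs**

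- Scans at week 9 and every 6 weeks after that (SAP 6.2.2.5). The second planned scan is 9 + 6 = week 15, which agrees with the 15-week limit in Table 3.
- A PR needs two determinations at least 4 weeks apart (SAP 6.2.2.1). With scheduled scans, the earliest confirmation of a week-9 response is week 15.
- PFS in months = (days from start to event or censoring + 1) / 30.4375.
- Assumed patient: PR from week 9, PD at week 51, every scan adequate and exactly on schedule.
- Assumed order: a scan on the day of surgery counts as before it. The SAP does not settle this, and a biopsy done at the time of the week-9 scan makes such a tie likely.

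**Results if the record is on the Concomitant Surgery page with a qualifying outcome**

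| Surgery | Scans used | Confirmed response | PFS |
|---|---|---|---|
| Not counted as new therapy | all | yes | event, (357 + 1)/30.4375 = 11.76 months |
| Excision after the week-9 scan | week 9 | no | censored, (63 + 1)/30.4375 = 2.10 months |
| Excision just before the week-9 scan | none | no | censored at start, 1/30.4375 = 0.03 months |
| Resection at week 12 | week 9 | no | censored, 2.10 months |
| Resection at week 16 | weeks 9, 15 | yes | censored, (105 + 1)/30.4375 = 3.48 months |

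If the first PR is at week 15 and the resection at week 16, the response is unconfirmed and PFS is again censored at 3.48 months.

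**What follows**

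1. In every counted case the PD at week 51 is discarded. After a week-9 excision, follow-up ends before the first PFS landmark of 3 months.
2. Response is lost only when surgery precedes the confirming scan. In the week-16 case with a week-9 PR, the response stands, but DR is censored at (42 + 1)/30.4375 = 1.41 months, where the PD would give (294 + 1)/30.4375 = 9.69 months.

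**Where Appendix 1 of the protocol intervenes.** It makes target status Indeterminate when a target lesion has been excised and has not reappeared or increased, provided that progression has not been documented. Under that rule the week-15 PR might not exist whatever 5.2.6 says. Protocol 7.9 instead takes a biopsied lesion out of the target set, which would leave a week-15 response possible. The loss of response can therefore be put down to 5.2.6 only when the excised lesion is not a target lesion, or when 7.9 is the rule applied. If Indeterminate is read as not evaluable in the SAP, a PD after two or more such scans would also be censored under Table 3 regardless of the surgery rule.

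**The case against.** The strongest reply is that the surgery page may itself be the filter. Drug and radiation records come from mixed pages and need sorting. Surgery has its own page with a coded outcome, and SAP 6.5.1.4 uses the matching prior-surgery page as a source of prior anti-cancer therapy. SAP 6.5.4 takes concurrent procedures from the non-drug treatment page, and the example in protocol 8.7 records a non-cancer operation as treatment of the adverse event. Neither document shows a biopsy being entered as surgery or coded Resected. This stands: whether the rule is ever triggered wrongly is unknown, and general surgery seems to be directed elsewhere. It does not remove the gap, because the page's scope is not stated and 6.5.5 itself subjects that page to clinical review.

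A second reply is that 6.5.5 supplies the missing review. It does for the listing. Its censoring sentence points back to 5.2.6, so the listing and the censoring variable could disagree for the same patient.

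A third is that efficacy here is secondary and descriptive, with no hypothesis test, and that censoring reasons are tabulated and listed. That limits the stakes and makes an error easier to spot.

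Three stronger readings are tempting, and the documents do not support them:

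- **The mandated biopsy itself biases the results.** The protocol mandates a biopsy, not an excision, and the effect also needs entry on that page with a qualifying code.
- **The response rate falls in proportion to the share of patients excised.** That share is not given, and Appendix 1 may already remove some of those responses.
- **Any resection turns a responder into a non-responder.** A response confirmed before the surgery is kept.

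**Conclusion.** The point holds as a defect in a stated rule whose practical effect is conditional. SAP 5.2.6 omits for surgery the clinical-review condition that it gives to drug and radiation, and that 6.5.5 gives to the same page. Followed literally, it can treat a diagnostic or other non-therapeutic resection as new anti-cancer therapy.

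For an affected patient the effect is large: PFS is cut to about 2.10 months or to the start date for a week-9 excision, later progression is dropped, and a response not yet confirmed can be lost. Each response lost in this way lowers the reported rate by 1/n, where n is the cohort size, which the documents do not fix.

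Across the trial the size cannot be given. It rests on how many such procedures are entered on the Concomitant Surgery page as Resected or Partially Resected, which may be none. The part that concerns response also rests on whether the excised lesion was a target lesion and on which of protocol 7.9 and Appendix 1 is applied.

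**What to change.** Replace the surgery bullet in SAP 5.2.6 with wording such as:

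> Date of surgery identified by clinical review as anti-cancer surgery, from the Concomitant Surgery page with outcome Resected or Partially Resected. Protocol-required or diagnostic biopsies and non-cancer procedures are not new anti-cancer therapy.

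Make 6.5.5 refer to the same reviewed set of records, so that the listing and the censoring date agree.

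The cost is one sentence in the SAP and a review of what should be few surgery records, on a page that 6.5.5 already puts under clinical review. If no biopsy or non-therapeutic resection was entered there, no result changes. The amendment does not settle how response is read after a target lesion is excised; that depends on protocol 7.9 and Appendix 1.

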### 5.2.7. Definition of On-treatment Period

Safety endpoints will be summarized based on the on-treatment period unless otherwise specified.

On-treatment period is defined as the time from the first dose of study treatment through minimum (30 days + last dose of study treatment, start day of new anti-cancer drug therapy – 1 day).

Safety data collected outside the on-treatment period as described above will be listed and flagged in listings but not summarized.

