20. **Adverse Event (AE) Assessments:** Adverse events should be documented and recorded at each visit using NCI CTCAE version 4.03. Patients must be followed for AEs for 28 days after the last treatment administration or until all drug related toxicities have resolved, whichever is later; or earlier than 28 days should the patient commence another anticancer therapy in the meantime. For serious adverse events (SAEs), the active reporting period to Pfizer or its designated representative begins from the time that the patient provides informed consent, which is obtained prior to the patient's participation in the study, ie, prior to undergoing any study-related procedure and/or receiving investigational product, through and including 90 calendar days after the last administration of the investigational products and before initiation of a new anti-cancer treatment. The prolonged follow up is due to the pharmacokinetic properties of the investigational product MK-3475. SAEs experienced by a patient after the active reporting period (see [Section 8.2](#)) has ended should be reported to the Sponsor if the Investigator becomes aware of them; at a minimum, all SAEs that the Investigator believes have at least a reasonable possibility of being related to study drug are to be reported to the Sponsor. AEs (serious and non-serious) should be recorded on the Case Report Form (CRF) from the time the patient has taken at least one dose of study treatment through last patient visit (Day 28 after last dose). If a patient begins a new anticancer therapy, the AE reporting period for non-serious AEs ends at the time the new treatment is started. Pregnancy or breast feeding that occur during the trial, within 120 days of discontinuing treatment with MK-3475, or within 28 days after the cessation of study treatment if the patient begins a new anticancer therapy, whichever is earlier, should be reported as in [Section 8.10](#) (Exposure During Pregnancy).
21. **Concomitant Medications:** All concomitant medications including supportive care drugs (eg, anti-emetic treatment and prophylaxis), and the drugs used to treat AEs or chronic diseases should be recorded in the CRF.

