Events of clinical interest of a potential immunologic etiology (irECIs) may be defined as an adverse event of unknown etiology, associated with drug exposure and is consistent with an immune phenomenon. irAEs may be predicted based on the nature of the MK-3475 and/or PF-05082566 mAb, their mechanism of action, and reported experience with immunotherapies that have similar mechanisms of action. Specific irAEs for MK-3475 and associated AE reporting requirements are listed in [Section 7.1.2.1](#). No irAEs have been observed with PF-05082566 to date. However, it is suggested that special attention should be paid to AEs that may be suggestive of potential irAEs related to both study drugs. An irAE can occur shortly after the first dose of either study drug or several months after the last dose of treatment.

If an irAE is suspected, efforts should be made to rule out neoplastic, infectious, metabolic, toxin or other etiologic causes prior to labeling an adverse event as an irAE. Information on how to identify and evaluate irAEs has been developed and is included in the Event of Clinical Interest and Immune-Related Adverse Event Guidance Document located in the Administrative Binder. Patients who develop a Grade 2 or higher irAE should be discussed immediately with the Sponsor.

Recommendations to managing irAEs not detailed elsewhere in the protocol are detailed in Table 9. If a decision is made to re-start treatment following irAEs, the PF-05082566 dose may be decreased one dose level (see [Table 7](#)). Patients treated at 2 mg/kg MK-3475 may be dose reduced to 1 mg/kg MK-3475 due to irAEs possibly attributed to MK-3475 alone. Once a patient has a dose reduction in PF-05082566 or MK-3475 for a drug-related toxicity, the dose will not be re-escalated. Patients requiring more than one dose reduction will be withdrawn from treatment unless otherwise agreed between the Investigator and the Sponsor.

Table 9. General Approach to Handling irAEs

irAE	Management of Both Study Drugs	Supportive Care
Grade 1	No action	Provide symptomatic treatment
Grade 2	May withhold	Consider systemic corticosteroids in addition to appropriate symptomatic treatment

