6.2. Study Period

For treatment period procedures, see the [Schedule Of Activities](#) and [ASSESSMENTS](#) sections. The End of Treatment assessments are to be performed approximately 28 days after the last dose of study drug. Obtain these assessments if not completed during the previous week on study (during the previous 6 weeks on study for tumor assessments).

Patients whose disease has not progressed at the end of treatment will enter into disease follow-up. During this follow-up period, patients will have disease assessments performed every 12 weeks \pm 7-days. Once patients have exhibited disease progression or began a new anti-cancer therapy (not including radiotherapy to a non-target tumor), whichever occurs first, the date of progression will be recorded on the appropriate CRF page and they will be withdrawn from the study. No further data will be collected from these patients. Patients continuing to experience treatment-related toxicity following discontinuation of study treatment will continue to be followed at least every 4 weeks until resolution or determination, in the clinical judgment of the Investigator, that no further improvement is expected.

For follow-up procedures see [Schedule Of Activities](#).

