indicate a possible immune-related ECI, then additional testing should be performed to rule out other etiologic causes. If no other cause is found, then it is assumed to be immune-related.

ECIs that occur to any patient from the date of first dose through 90 days following cessation of treatment, or the initiation of a new anticancer therapy, whichever is earlier, whether or not related to the Sponsor's product, must be reported within 24 hours to the Sponsor either by electronic media or paper. Sponsor Contact information can be found in the administrative binder.

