8.2. Reporting Period

For SAEs, the active reporting period to Pfizer or its designated representative begins from the time that the patient provides informed consent, which is obtained prior to the patient's participation in the study, ie, prior to undergoing any study-related procedure and/or receiving investigational product, through and including 90 calendar days after the last administration of study drug. SAEs occurring to a patient after the active reporting period has ended should be reported to the Sponsor if the investigator becomes aware of them; at a minimum, all SAEs that the investigator believes have at least a reasonable possibility of being related to study drug are to be reported to the Sponsor.

AEs (serious and nonserious) should be recorded on the Case Report Form (CRF) from the time the subject has taken at least 1 dose of study treatment through the last subject visit.

If a patient begins a new anticancer therapy, the AE reporting period for non-serious AEs ends at the time the new treatment is started. Death must be reported if it occurs during the SAE reporting period after the last dose of investigational product, irrespective of any intervening treatment.

Pregnancy or breast feeding that occur during the trial, within 120 days of discontinuing treatment with MK-3475, or within 28 days after the cessation of study treatment if the patient begins a new anticancer therapy, whichever is earlier, should be reported as in [Section 8.10](#) (Exposure During Pregnancy).

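### SAEs and events of clinical interest are reportable to 90 days after the last dose, but the SAP summarises safety only to 30 days, so later ones appear in flagged listings and in no frequency table

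*SAP*

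**What the plan says.** **Reporting.** Protocol Schedule of Activities, footnote 20, runs SAE reporting "through and including 90 calendar days after the last administration of the investigational products", adds that it applies before a new anti-cancer treatment is started, and gives the reason: "The prolonged follow up is due to the pharmacokinetic properties of the investigational product MK-3475". Protocol 8.2 repeats the window, "through and including 90 calendar days after the last administration of study drug", without the new-treatment limit. Protocol 7.1.2.1 covers "ECIs that occur to any patient from the date of first dose through 90 days following cessation of treatment", or to new anticancer therapy if that comes first. On immune-related events (irAEs), Protocol 5.3.7.2 warns: "An irAE can occur shortly after the first dose of either study drug or several months after the last dose of treatment".

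**CRF recording.** Footnote 20 has adverse events, serious and non-serious, recorded on the CRF "from the time the patient has taken at least one dose of study treatment through last patient visit (Day 28 after last dose"). Protocol 8.2 names the last subject visit and gives no day. Under Protocol 7.1.2.1, ECIs go on the adverse event CRF.

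**Analysis.** SAP 2 bases the analyses on cleaned eCRF data plus non-CRF data such as PK and biomarkers. SAP 5.2.7 ends the on-treatment period at the last dose plus 30 days, or the day before new anti-cancer drug therapy, and then says: "Safety data collected outside the on-treatment period as described above will be listed and flagged in listings but not summarized". The SAE tables in SAP 6.6.3 and the irAE tables in 6.6.4 are limited to treatment-emergent events, while the listings in those sections include late onsets with a flag. SAP 6.6.2 tabulates all deaths as well as deaths within 30 days.

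**End of follow-up.** Protocol 6.2 withdraws patients in disease follow-up once they progress or start new therapy, and says: "No further data will be collected from these patients".

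**The concern.** The protocol lengthens SAE follow-up for a pharmacological reason and expects irAEs months after treatment. The SAP then applies a 30-day window to every SAE and irAE frequency. A reader of the tables would see rates by dose group that leave out events the sponsor chose to collect, and would have to count those events by hand from listings.

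The overall safety profile of the combination is a secondary objective. SAP 2.2 also says that expansion-cohort safety data will support the choice of the recommended Phase 2 dose.

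The listings may themselves be incomplete. If CRF recording of SAEs stops at Day 28, an SAE on day 60 that is not an ECI could sit in the safety database and be absent from an eCRF-based listing. Sites also have conflicting instructions on what to collect once a patient in disease follow-up has progressed or started new therapy.

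**Working it through.** **1. The windows side by side (days after last dose).**

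| Item | Ends at | Source |
|---|---|---|
| SAE reporting | 90; footnote 20 also stops at new anti-cancer treatment, 8.2 does not | Footnote 20; Protocol 8.2 |
| ECI reporting | 90, or new anticancer therapy if earlier | Protocol 7.1.2.1 |
| CRF recording, serious and non-serious | 28, or last subject visit | Footnote 20; Protocol 8.2 |
| SAP summary tables | 30, or day before new anti-cancer drug therapy | SAP 5.2.7 |
| SAP listings | no limit; late onsets flagged | SAP 6.6.1, 6.6.3, 6.6.4 |
| Death table | no limit | SAP 6.6.2 |

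**2. Size of the gap in time.** 90 − 30 = 60 days, and 60/90 = 66.7% of the post-dose reportable days. This applies to a patient with no new therapy. If new drug therapy starts on day d:

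- With d from 31 to 90, footnote 20 and Protocol 7.1.2.1 leave a gap of d − 31 days. Protocol 8.2 leaves 60 days for SAEs.
- With d of 30 or less, footnote 20 and 7.1.2.1 leave essentially no gap. Protocol 8.2 leaves 91 − d days for SAEs.

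The size therefore depends on which SAE rule applies, and the protocol does not settle that.

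**3. Drug remaining.** Protocol 1.2.9.1.1 gives MK-3475 a half-life of 21 days. Assuming simple exponential decline, the fraction left is 0.5^(day/21). That is 0.5^(30/21) = 0.37 at day 30 and 0.5^(90/21) = 0.05 at day 90. This agrees with the protocol's reason for a window beyond 30 days, but says nothing about event rates.

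**4. The plan's own detection figure.** Protocol 9.3 says that 45 patients detect a 5% toxicity with probability 0.90 and a 10% toxicity with 0.99. The formula is 1 − (1 − p)^45:

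- p = 0.05: 1 − 0.95^45 = 0.9006
- p = 0.10: 1 − 0.90^45 = 0.9913

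Both reproduce.

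**5. What the tabulation window could do to that figure.** Let f be the share of affected patients whose first event falls after the summarised window. The documents give no value for f, so a range is shown. The chance of at least one tabulated case is 1 − (1 − p(1 − f))^45.

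| Assumed f | p = 5% | p = 10% |
|---|---|---|
| 0 | 0.90 | 0.99 |
| 10% | 0.87 | 0.99 |
| 20% | 0.84 | 0.98 |
| 30% | 0.80 | 0.96 |
| 50% | 0.68 | 0.90 |

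A 90-day table recovers the top row only if the late onsets fall by day 90, are SAEs or ECIs, and are recorded in the data analysed.

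**6. Protocol 6.2 against the later duties.** The data stop follows a sentence that sends patients without progression at end of treatment into disease follow-up, so it is written for those patients. The next sentence continues follow-up of ongoing treatment-related toxicity. That exception does not cover a new event starting after progression. The 90-day SAE and ECI duties (8.2, 7.1.2.1) and the 3- and 6-month MK-3475 PK and anti-drug antibody samples (7.2.2, 7.5.2) are not made conditional on progression. Footnote 32 evaluates patients up to 90 days, yet also withdraws them at progression or new therapy. For a patient who progresses or starts new therapy during disease follow-up, these instructions cannot all be followed as written.

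**The case against.** The case for leaving the plan alone has real force.

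- **Late events are not discarded.** A reader might infer that late immune toxicity is lost from the safety report. The documents do not support that: captured SAEs and irAEs after day 30 are listed with a flag, and all deaths are tabulated.
- **The tables are correct for what they define.** They are labelled treatment-emergent and match the SAP's definition. In an escalation phase of at most 45 patients with no hypothesis test, a flagged listing can be read directly. This weakens for the expansion cohorts, whose size is left open.
- **Protocol 6.2 does not stop all data at progression.** That reading is tempting, but the sentence concerns patients in disease follow-up, and ongoing toxicity is still followed. Nor can one say the conflict will be common: patients who stop treatment because of progression do not enter disease follow-up, and no frequency is given.
- **The 67% is a share of calendar days, not of events.** It takes no account of up to 32 cycles of tabulated treatment time.
- **Dose selection does not hang on these tables.** The MTD rests on first-two-cycle DLTs in the TITE-CRM, expansion DLT data feed the same model (Protocol 3.7), and the sponsor's safety review draws on the safety and clinical databases (Protocol 9.7).

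Each of these narrows the point. None explains why a window set at 90 days for collection has no matching summary, and none resolves the Day 28 CRF limit or the wording of Protocol 6.2.

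**Conclusion.** The mismatch is real, and the remedy is an inexpensive improvement rather than the correction of a wrong analysis. SAEs and ECIs with onset on days 31 to 90 are collected by design but contribute to no frequency by dose group. Deaths are not affected.

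The gap is 60 of 90 reportable days for a patient without new therapy. Its effect on event rates cannot be stated, because the documents give no late share. If 10% to 50% of first onsets were late, the chance that a 5% toxicity reaches a table would fall from 0.90 to between 0.87 and 0.68. That range is an illustration. It does not show that the reported rates will be understated by any given amount.

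The 90-day duty covers SAEs and ECIs only. Footnote 20 ends CRF recording at Day 28 for a non-serious irAE that is not an ECI, so it would be wrong to treat all irAEs as collected to 90 days. The same Day 28 limit means that some non-ECI SAEs after that day may be missing even from the listings. The documents leave this possible but do not establish it.

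**What to change.** 1. **SAP 5.2.7, 6.6.3 and 6.6.4.** Keep the 30-day tables. Beside them add supplementary tables of SAEs and of ECIs (including serious irAEs) through 90 days after the last dose, by treatment group, flagging events that start after new anti-cancer therapy. Label them as covering SAEs and ECIs, not all irAEs.
2. **Protocol footnote 20 and Section 8.2.** Align the CRF recording period for SAEs and ECIs with the 90-day window, so that the tables and listings rest on complete data.
3. **Protocol 6.2 and footnote 32.** Reconcile them with Sections 7.1.2.1, 7.2.2, 7.5.2 and 8.2, so that it is clear what is still collected after progression or new therapy. State whether SAE reporting ends at new anti-cancer therapy, on which footnote 20 and Section 8.2 differ.

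The cost is a few extra tables, a protocol clarification and a longer CRF period for a limited set of events. Some late events will be confounded by subsequent therapy, which is why the flag is needed. The existing 30-day analysis is unchanged.
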